[name], Paediatric Research Nurse, Lancashire Teaching Hospitals NHS Trust. [name] is a nurse in Child Health Department at Royal Preston Hospital. She is a research nurse, and also works as a neonatal nurse on the level 3 neonatal unit. She has been involved with a number of studies in children and neonates. Together with [name], [name] is about to start an exciting study looking at determinants of activity in children with muscle conditions. Supporting the clinical physiotherapist, [name] will be involved in the set up recruitment and management of the study.

[name], Research Operations Manager, Lancashire Teaching Hospitals NHS Trust. [name] represents the LTHTR trust as the sponsor for this study.

Background (*Literature review*):

There is a doubling of body fat (BF%) in young males with Duchenne Muscular Dystrophy (DMD) (Mayo et al., 2012), which may represent a significant contributory factor to comorbidities associated with this untreatable neuromuscular condition. In adults with DMD and BMD we have found that, a higher BF% is associated with impaired glucose tolerance (Bostock et al., 2018) and lower perceived quality of life (QoL, Jacques, Stockley, Onambele-Pearson, et al., 2019). Similarly, boys and adolescents with DMD have lower perceived QoL (Kohler et al., 2005), and can show evidence of mental health issues (Steele et al., 2008) commonly associated with progressive disability. This progressive physical impairment, coupled with high levels of bodily pain (Hunt et al., 2016), likely contributes to boys and adolescents with DMD having lower daily physical activity levels and subsequently higher BF% and BMI than age matched boys without DMD (McDonald et al., 2005). Furthermore, an accumulating BF% in boys and adolescents with DMD may accentuate functional impairments such as lower limb weakness, as anti-gravity muscles are having to overcome an increasing body mass.

Within boys with DMD, hydrotherapy is recommended (Bushby et al., 2005), yet in contrast to other neuromuscular conditions, within DMD there is scant evidence that hydrotherapy benefits QoL, pain and mobility. These quantifiable outcome measures have all shown benefit from longitudinal hydrotherapy in other populations including fibromyalgia, osteoarthritis, stroke and spinal muscle atrophy (Karjalainen et al., 1999; de Mattos et al., 2016; Marinho-Buzelli et al., 2014). Within DMD, data is limited to small participant numbers, with some benefit of hydrotherapy shown in 1, 6 or 8 boys, compared to 2-6 boys not receiving the treatment (Honório et al., 2013; Honório, 2011; Hind et al., 2017). Where smaller groups of data are presented e.g., 8 boys with DMD receiving hydrotherapy, the focus was on 6-minute walk distance, rather than QoL or pain, and was again limited to comparisons with 2 control participants (Hind et al., 2017). In contrast, within Spinal muscle atrophy, improvements in QoL have been reported with frequent hydrotherapy (Cunha et al., 1996).

Despite evidence that low intensity exercise may benefit, or at least not negatively impact, physical function and daily pain in DMD (Hunt et al., 2016; Jansen et al., 2013), there is at present a lack of evidence to suggest that those with DMD should undertake hydrotherapy, despite favourable anecdote (MDUK, 2015) and case reports. Previously, we have identified a modest metabolic response following low intensity hand cycling in non-ambulatory men with DMD ([name] et al., 2018). This cardiorespiratory impact was however, limited to those with the most functional upper limbs. Specifically, of those completing the study 2 men aged 18 and 20 were able to increase their metabolic rate to a level that would induce a meaningful health benefit. It could be hypothesized therefore, that young males (aged 6-18) with DMD have the potential to induce health benefits from active hydrotherapy movements. In contrast, those with limited mobility or active musculature, may experience benefits from passive hydrotherapy (e.g. pain and joint mobility). An exercise diary will be recorded for every hydrotherapy session, and with a sufficient sample of 20 participants, it will be possible to analyse the results of the study as a single intervention group with exercise intensity as a covariate to outcome adaptation, consistent with our previous sedentary behaviour interventions in other populations (Ryan et al.,

2018). This project therefore seeks to: 1) undertake a hydrotherapy intervention in boys and adolescents with DMD and 2) conduct qualitative Patient and Parent interviews to understand the potential barriers and hidden benefits to hydrotherapy not captured in our outcome measures.

Research Objective:

It is hypothesised that undertaking hydrotherapy will result in a beneficial change in the primary outcomes of QoL, bodily pain, and body composition, and secondary outcomes of physical function (e.g. Range of motion strength, and upper limb function), where possible.

The **aim** of this study is to determine whether hydrotherapy can mitigate some of the weight gain, bodily pain, lower QoL and functional impairments associated with progression of DMD in young males.

Potential outcomes include:

- 1) improvements in all outcome measures as a result of undertaking hydrotherapy (increased lean muscle mass, reduced body fat; improved functional measures (e.g. strength), activities of daily living, ROM; improved quality of life, and lowered bodily pain).
- 2) no change in outcome measures following hydrotherapy but a relative slowing of the decline observed during the “control period”.
- 3) outcome measures continue to deteriorate at the same rate as the control period.
- 4) a worsening of outcome measures compared to the control period.

Objectives and Specific Aims:

Outcomes

This project will yield 4 experimental journal articles.

1. The impact of hydrotherapy on body composition and muscle mass in boys with DMD
2. The impact of hydrotherapy on QoL and bodily pain in boys with DMD
3. The impact of hydrotherapy on muscle function and activities of daily living in boys with DMD
4. Practical considerations and barriers to hydrotherapy in young people with DMD, a qualitative review of interviews with parents, carers and those with DMD.

As the first hydrotherapy study within DMD, the overarching outcome will be to determine whether it is efficacious and beneficial to complete a longitudinal hydrotherapy intervention in young males with DMD, which will inform future guidelines on activity within this population. To this end we will conduct qualitative interviews and work alongside the members of the Northwest Neuromuscular network, and the Neuromuscular Centre (Winsford, UK) who regularly undertake hydrotherapy to engage with service users with DMD to provide guidelines for physical activity based on our previous work on sedentary behaviour (Jacques et al., 2018) and the findings of this proposed project.

Qualitative interviews

Face-to-face interviews will be conducted with 20 participants from the study. This will include a mixture of those with DMD, and their parents, to understand what barriers are faced when undertaking hydrotherapy, what about the hydrotherapy intervention was suitable, and whether there are benefits to hydrotherapy not captured in our outcome measures (Bagley et al., 2016). The interviews will be approached from an interpretivist perspective to make sense of the lived

experiences of those involved in the hydrotherapy (Schwartz-Shea and Yanow, 2013), consistent with the expertise within our research team. In addition to a scientific publication, these qualitative findings will inform the development of future guidelines on hydrotherapy and allow us to optimise participant benefit through relevant research.

Rationale and Significance of Study:

Protocol design justification

While natural history studies indicate an overall negative trend in the abilities of patients with DMD, there is great variability in age and speed of deterioration (Muntoni et al., 2019). As such it is difficult to find matched controls for a short randomised intervention study. Instead, due to the progressive nature of DMD and the inherent variance within a mixed age, and ability population (e.g. upper limb & respiratory function, genetic variation etc.(Ricotti et al., 2019)), the participants will act as their own controls. This single-arm, non-crossover design where the participant acts as his own control, although not as robust as randomized control exercise trials, is advocated for longitudinal interventions in populations such as the present one (Hecksteden et al., 2018). Indeed, this self-controlled approach offers some of the benefits of prospective controlled trials, allows for multiple treatments within the same participants, and eliminates some of the covariates of group comparisons which are inherent in dual arm training studies (Vohra et al., 2015). Specifically with treatments such as hydrotherapy, the process of randomisation leads to patient and parent disengagement due to not getting to undertake a treatment (Hind et al., 2017). This self-controlled study avoids the downsides of randomisation for the participants and is consistent with previous exercise training studies both in non-clinical (Narici et al., 1989), and in our own training studies in muscular dystrophy (Bostock et al., 2019).

Research Design

The **aim** of this project is to undertake 12-weeks of hydrotherapy in boys and adolescents with DMD, and monitor the impact on body composition, bodily pain, QoL and physical function. The project is broken down into 3 key stages:

Pre-experimental stage: during this stage we will secure ethical approval, and recruit participants. This stage will last ~6 months due to the length of time it takes to secure NHS ethical approval.

Experimental stage: the participants will complete the experimental protocol described below in detail. Briefly, participants will complete TWO 12-week periods. The first will be an observation (control) period to use as a reference point for the second period, which will involve 12-weeks of hydrotherapy. *Figure 1* attached describes the testing sessions; these will be completed at 3 time points, the first before the control period, the second after the control period, and the third after the hydrotherapy period. The experimental stage will last 28-months due to the staggered recruitment and testing of participants.

Post experimental stage: this stage will involve the analysis of data and production of academic papers for submission within international journals. This stage will be scheduled for 4-months but will continue until the data has been published. Although the cost of a dissemination event is not formally included within this bid; as researchers and clinicians we regularly update physiotherapists, carers, clinicians and those with DMD through dissemination events. We plan to present our findings at events hosted through the

Northwest Neuromuscular Network, The Neuromuscular Centre outreach and dissemination days, and through the hospice website.

Experimental stage protocol

Participants will complete two 12-week periods, including an initial control period (CTRL), where they will undertake their habitual physical activity behaviour. This will be followed by 12-weeks of hydrotherapy, where participants will complete up to 60 mins of hydrotherapy once a week. During these CTRL and hydrotherapy periods, diet and physical activity will be monitored to identify any lifestyle covariates that could contribute to their body composition and physical and mental wellbeing. Pre and Post CTRL, and Post hydrotherapy, participant outcome measures will be re-assessed.

Consent: consent will be obtained from patients 16 years and older or parents / guardians of children younger than 16 years of age, either face to face or via a pre-arranged video link with a member of the research team who is signed off the delegation log as being able to take consent.

If consent is taking place face to face, a suitable time will be arranged between a member of the research team and the family. Consent can take place during the patient's usual Neuromuscular clinic or at an independent appointment at the Clinical Research Facility (CRF). This is also a good opportunity for the young person to familiarise themselves with the CRF.

If consent is taking place via a pre-arranged video link, a suitable time will be arranged between patient/parents/guardians and a member of the research team. Microsoft Teams, Attend Anywhere or Zoom are acceptable platforms that can be used depending on individual Trust guidelines. A copy of the PIS and the appropriate consent form (with all details completed by Research Team as needed) will be posted to the family with a pre-paid return envelope.

During the consent appointment, either face to face or via video link:

1. A member of the research team will confirm they have received the PIS, have read it and have understood it.
2. Patient/ Parents / guardians will be asked if they have any questions.
3. Questions will be answered until they are content.
4. The research team member taking consent will re-confirm the fact that the child can be withdrawn at any time without giving any reasons and that this will not affect the physiotherapy treatment the child receives.
5. The patient/parents/guardians will then be given the consent forms. They will be asked to read every statement, initial each box, and sign and date at the end of the form.
6. The research team member taking consent will then sign and date the form. If appointment is completed via video link, the wet ink copy is posted back to the research team to sign and date and note that the form was completed by parents during the video link.
7. The wet ink copy will be kept by the research team member.

8. A copy of the signed consent will be given to the patient/ parents / guardian to keep for their own records. If via video link, this copy will be posted to parents or given when the family attend for their initial assessment.

Participants and power calculation

We are adopting an inclusive approach to participant recruitment, which is possible through the within group design of the control and hydrotherapy interventions. To this end, we aim to recruit 44 male participants aged over 6 years of age, who have previously been diagnosed with DMD from multiple neuromuscular centres in the Northwest Neuromuscular Network (Royal Preston, Manchester, Alder Hey, Oswestry) and from Derian House Children's Hospice (Chorley, UK). Participants will be included if they are able to undertake a single bout of hydrotherapy lasting at least 45 minutes, and are not currently ventilated during the day. An initial assessment will be performed by the clinical physiotherapist associated with the project (See attached *Figure 2-Gant Chart*). Exclusion criteria will include any regular hydrotherapy exercise within the preceding 12 weeks.

There are at present limited data on the effect of hydrotherapy on QoL in DMD from which to base a power analysis, therefore we have carried out our analysis using a previous hydrotherapy intervention in adults with Osteoarthritis (Fransen et al., 2007). It should be noted that their pre intervention QoL scores were similar to those we have collected in DMD participants [DMD = 34.3(5.9), Osteoarthritis = 31.9 (8.5), (Means(SD))].

Within their 24 sessions of hydrotherapy, Fransen et al (2007) report effect sizes above that of control of 4.0, with no change in their control group. If we make the assumption that within our 12 session intervention we are likely to see half of the improvement in QoL, we shall base our power analysis of an effect size of 2 compared to that of controls. With the following values, within participant *apriori* power calculation performed using G*Power (Version 3.1.7, University of Kiel, Germany) suggests a total group number of n = 8 (α err prob=0.05, Power 0.95). We feel this is too conservative given that we also need to a) account for drop-out of participants and b) fulfil the criteria for parametricity in a clinical condition that has a wide variance (children and adults with DMD ranging from 6-25 yrs are very varied in the presentation of physical function). Therefore, given the aforementioned considerations and as this is a novel intervention in terms of research outcomes and will serve as a primary point of reference for subsequent hydrotherapy studies within DMD, we will recruit 44 participants in total.(See also *table 1*, summarising published hydrotherapy trials in similar medical conditions)

Participants will be recruited through the respective neuromuscular clinic and through Derian House hospice.

Inclusion criteria

- Established diagnosis of Duchenne Muscular Dystrophy (either by genetics or muscle biopsy)
- Between 6 and 25 years of age
- On stable dose of steroids or not on steroids

Exclusion criteria

- Younger than 6 years, older than 25 years
- Recent change in steroid dose, less than 3 months prior
- Undertaking formal hydrotherapy supervised by physiotherapist on a regular basis (weekly or more frequent)

Body composition

Fat mass, body fat percentage and fat free mass will be measured using bioelectrical impedance (BIA). Although more stringent measures of body composition exist such as dual-energy X-ray absorptiometry (DEXA), BIA has been validated in DMD and is accurate enough to measure longitudinal changes in body composition and muscle mass in this population (Mok et al., 2010; Kuru et al., 2019).

Physical function

Established physical function assessments for individuals with neuromuscular conditions will be completed. These will include the North-Star and Performance of the Upper Limb assessment (Mayhew et al., 2013); and an assessment of activities of daily living (Wu et al., 2011).

Limited ankle range of motion (ROM) has long been recognised as a characteristic of children with DMD (Archibald and Vignos, 1959). Hydrotherapy has proven successful to offset impairments in children with ankle contractures albeit with Cerebral palsy (Kesiktas et al., 2004); ankle plantarflexion-dorsiflexion (PF-DF ROM) will be assessed through a goniometer.

Grip and pinch strength will also be assessed using digital, handheld dynamometers.

Pulmonary function

Participants will complete lung function measures using digital spirometry.

Mental wellbeing, QoL and pain

The PedsQL QoL questionnaire will be used to assess QoL, as it is a reliable measure of disease-specific health-related QoL in those with DMD from childhood to 18 yrs of age (Davis et al., 2010). In addition we will use the PedsQL multidimensional fatigue scale. We will also use the DMD-QoL and DMD-QoL Proxy, a recently developed tool to measure quality of life in patients with DMD. In addition, a pain map assessment of the topographic distribution of daily pain will also be completed, consistent with our previous work in DMD (Jacques, Stockley, Bostock, et al., 2019). We will also include a participation measure (CASP)

Physical activity and diet

Triaxial accelerometers will aim to be worn for up to 7-days during the first week of CTRL and hydrotherapy. We have previously adopted this approach in adults with MD, and have reported meaningful associations between habitual PA and both QoL and ADL (Jacques et al., 2018).

Over 7-days during both CTRL and hydrotherapy periods, participants will record daily food intake for 3 days using a smartphone app. Subsequent analysis will be performed using dietary analysis software (Nutritics).

Intervention

During the 12-week hydrotherapy intervention, participants will complete a weekly hydrotherapy session lasting from 30 to 60 mins. This is a duration and frequency of

hydrotherapy consistent with previous studies that have shown improvements in QoL in fibromyalgia (Mannerkorpi et al., 2002), physical function in Parkinson's disease and multiple sclerosis (Salem et al., 2011; Vivas et al., 2011), and functional independence and mental health in adolescents with cerebral palsy (Dorval et al., 1996). An overview of previous studies and hydrotherapy parameters is provided in Table 1.

The exercises, intensity and specific hydrotherapy session plan will be derived from consultation between the participants, and clinical physiotherapist. Due to the variance within the presentation of the condition and the inclusive age range within the study, we will take what we consider as an externally valid approach to exercise prescription. We will record heart rate during a sample of the participants' hydrotherapy sessions, which will be included as a co-variate for subsequent analysis.

Hydrotherapy will be conducted at Derian House Children's Hospice (Chorley, UK), and may include weight-bearing activities such as standing and gait practice, assisted and resisted limb exercises. Core and trunk work including swimming.

Please find attached

Figure 1-experimental overview

Figure 2-GANTT chart

Figure 3- proposed experimental workflow

Table 1 -current research in hydrotherapy

Data Analysis:

All participants will be assessed using a repeated measures design. Given the broad heterogeneity of DMD participants recruited there is no meaningful benefit of intergroup comparisons between those participants who can complete 30-60 mins of active hydrotherapy, compared to those who can perform arm only, or passive hydrotherapy. Experimentally it is not of interest if one group changes more than another, it is of interest if there is a change within the individuals themselves. We have recently completed a resistance training protocol in adults with MD and adopted a similar approach (Bostock et al., 2019).

Participants will be assessed against previous time points (Pre-CTRL vs Post-CTRL vs Post hydrotherapy) using repeated measures Anova (where outcomes are parametric) or Friedman's (where parametric assumptions are violated). Tests of association will be used to compare relative hydrotherapy intensity with changes from PRE to Post hydrotherapy.

Adverse Events:

All adverse events will be reported to the Chief Investigator and study Sponsor. Depending on the nature of the event the reporting procedures below will be followed. Any questions concerning adverse event reporting will be directed to the Chief Investigator in the first instance.

Adverse Events

If an incident needs acute attention, a member of the research team will follow local emergency procedures.

These will be recorded using the Adverse Event Reporting form, discussed with CI and paediatricians/ physiotherapist of team and escalated to the study Sponsor.

Serious Adverse Events

No SAE is anticipated, however, in the event of a suspected SAE occurring a form will be completed by a member of the research team, who will then notify (in person or via Egress secure email) the Chief Investigator and Sponsor representative within 24 hours. The Chief Investigator and Sponsor will assess and determine if the SAE is related to the study procedures and report back to the research team via e-mail.

All SAEs will be reported to the ethics committee where, in the opinion of the Chief Investigator, the event was: 1 'related', i.e. resulted from the administration of any of the research procedures; and 2 'unexpected', i.e. an event that is not listed in the protocol as an expected occurrence. Reports of related and unexpected SAEs will be submitted within 15 days of the Chief Investigator becoming aware of the event, using the SAE form for non-IMP studies.

Monitoring:

The conduct and running of this research project will be overseen by the Chief Investigator which may be delegated to lead research physiotherapist. They will audit and monitor the research through all the stages and until completion on a risk assessed basis. The audit and monitoring process will be conducted in line with the terms of funding for the research and in line with LTHTR's policies, procedures, and the Research Governance Framework.

Local teams will also be answerable to their local R&D department, who will also monitor and audit all research undertaken at the Trust.

Dissemination:

The results of this study will be used to inform the neuromuscular service in Preston and at other sites in the UK. The results will also be shared more widely by presenting them at regional and or national meetings. The results may be published in a scientific journal and presented at scientific medical conferences and through publications and meetings organised by Duchenne UK. Outcomes will also be shared by DMD Care UK to help improve the standards of care. You will not be identified in any report or publication.

Ethical issues:

Ethical review and approval will be sought through an application through IRAS. (Reference 304633)

References:

Archibald, K. and Vignos, P. (1959) 'A study of contractures in muscular dystrophy.' *Arch Phys Med Rehabil*, 40(4) pp. 150-157.

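### Lean mass is tabulated in kilograms and compared as visit levels in participants aged 6 to 25, so ordinary growth can appear as improvement

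*Protocol*

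**What the plan says.** - **Outcome.** Research Objective names the "primary outcomes of QoL, bodily pain, and body composition". The first of its potential outcomes is improvement, which for body composition means "increased lean muscle mass, reduced body fat". The second is "a relative slowing of the decline observed during the" control period. The third and fourth are also worded against that period.
- **Measures.** The Body composition section says "Fat mass, body fat percentage and fat free mass will be measured using bioelectrical impedance (BIA"), without units or scaling. Figure 1 schedules BMI in kg/m², body fat as a percentage and LMM in kg, each at all three assessments. No height index, age standardisation or z-score is mentioned.
- **Population.** Inclusion criteria: "Between 6 and 25 years of age".
- **Design.** Of the two 12-week periods, Research Design says "The first will be an observation (control) period to use as a reference point for the second period".
- **Analysis.** Data Analysis says "Participants will be assessed against previous time points (Pre-CTRL vs Post-CTRL vs Post hydrotherapy) using repeated measures Anova", with Friedman's test if parametric assumptions fail. It names no contrast of the change in one period with the change in the other.

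**The concern.** Lean mass in kg rises with body size. Many participants will still be growing over the 24 weeks, while the oldest probably will not. A pooled mean in kg therefore mixes growth with change in composition, in a proportion set by the age mix. A test of visit levels responds to any trend over time, including steady growth that is the same in both periods.

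The potential outcomes other than improvement take decline as the untreated course. They do not provide for a measure that may rise untreated. If lean kilograms go up for reasons of growth, the natural place to file the result is the first outcome, improvement. One of the four planned papers is on body composition and muscle mass, so this could reach a main conclusion.

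**Working it through.** **The plan's own figure.** The protocol gives no growth rate, lean mass, variance or sample size for body composition. Its one calculation (n = 8) is for QoL at "α err prob=0.05, Power 0.95" and an effect size of 2. Read as a standardised paired difference, 2 gives n = 6 two-sided or 5 one-sided; a value of 1.5 two-sided gives 8. Nothing below depends on it.

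**Step 1: growth in one period.** Assumed, not from the protocol: height growth of 2-6 cm/year, constant lean mass per height squared, and two illustrative boys.

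Gain = L × [((h + Δh)/h)² − 1], with Δh = annual growth × 12/52, which is 0.46 cm at 2 cm/year and 1.38 cm at 6 cm/year.

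| Height, lean mass | 2 cm/year | 6 cm/year |
|---|---|---|
| 120 cm, 16 kg | 0.77% = 0.12 kg | 2.32% = 0.37 kg |
| 140 cm, 25 kg | 0.66% = 0.17 kg | 1.99% = 0.50 kg |
| Adult, no growth | 0 | 0 |

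The pooled mean is this gain times the share still growing. At an illustrative one half, it is 0.06-0.25 kg.

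**Step 2: what the stated test does with it.** Simulation with N = 44 (the planned number), linear growth, no hydrotherapy effect and 4,000 runs per setting. Assumed: between-participant slope SD 0.2 kg per period, and measurement SD 0.5 or 1.0 kg. Each cell gives the rejection rate at SD 0.5 / SD 1.0.

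| Mean growth per 12 weeks | ANOVA over three visits (nominal 5%) | Post hydrotherapy above Post-CTRL, paired (nominal 2.5%) | Change in hydrotherapy minus change in control (nominal 5%) |
|---|---|---|---|
| 0 kg | 4.9% / 4.6% | 2.3% / 2.2% | 4.7% / 5.2% |
| 0.1 kg | 31% / 12% | 14% / 6% | 4.8% / 5.0% |
| 0.2 kg | 86% / 35% | 42% / 15% | 5.1% / 5.0% |
| 0.3 kg | 99.8% / 67% | 75% / 28% | 5.1% / 5.8% |

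All columns use raw kg. Comparing levels inflates the error; contrasting the two changes does not, provided growth is steady.

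**Step 3: when growth is not steady.** Suppose a boy grows at 2 cm/year in the control period and 6 cm/year in the hydrotherapy period. By Step 1 the contrast of changes in kg is then off by about 0.37 − 0.12 = 0.25 kg for the smaller boy and 0.50 − 0.17 = 0.33 kg for the larger. A boy who slows down gives the opposite sign. Under the constant-index assumption, lean mass per height squared does not move in either case.

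**Step 4: price of the contrast.** In the Step 2 model a pre-post difference has variance 2σ² + 0.2², and the difference of changes has 6σ². The SDs are 0.73 against 1.22 kg at σ = 0.5, and 1.43 against 2.45 kg at σ = 1.0. The contrast is therefore about 1.7 times as wide.

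**The case against.** The strongest reply is that the design already deals with growth. The control period is there as a reference, the outcomes other than improvement are worded against it, and the improvement item is itself conditioned on hydrotherapy as the cause. It sits in a list of possible outcomes, with no unit, test or threshold, so it is not a decision rule. Three visits would also show a matching rise during the control period. Scaling and derived variables are often left to an SAP, which may supply them.

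Much of this stands. The control period can remove steady growth, even in kg. But the test written in Data Analysis compares levels and does not state the contrast that would do so. The protocol itself sets the lean-mass unit, the age range and the comparison.

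A reader might go further and infer any of the following, none of which the document supports:

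- *All of body composition is judged in kilograms.* Only LMM carries that unit. Body fat is scheduled as a percentage, and no unit is given for fat mass or fat-free mass.
- *The growth gain is the bias.* It occurs in both periods. Adding the two periods gives an upper figure near 1.0 kg, but that is not an error in any treatment contrast.
- *The bias favours hydrotherapy throughout.* That direction applies to lean mass. Growth in BMI or fat mass would tend to mask benefit.
- *Lean kilograms must rise.* The protocol describes DMD as progressive and gives no rate of muscle loss, so loss may offset or exceed growth.

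**Conclusion.** The point holds in limited form. Followed as written, the plan lets growth in lean kilograms register as a change over time, in the direction the protocol calls improvement. The size in a growing boy is about 0.12-0.50 kg per 12 weeks under the stated growth and scaling assumptions. It is zero in adults, and the pooled figure lies between, depending on age mix. The false-positive rates rest on assumed growth rates and SDs. They show the mechanism and do not forecast this trial.

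Most of the inflation comes from testing levels; the unit matters in addition when growth differs between periods. Net size and direction cannot be fixed from the protocol. The point affects one component of one primary domain, and body fat % remains usable. The change is worth making because it costs little.

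**What to change.** - Name body fat % and height-indexed fat-free (lean) mass as the analysed body-composition measures. Show raw kg descriptively only.
- Measure height, or one fixed surrogate for participants who cannot stand, by the same method at all three visits. BMI at each visit already needs a height.
- Test change during hydrotherapy minus change during control, (Post hydrotherapy − Post-CTRL) − (Post-CTRL − Pre-CTRL), and not levels alone.
- Give BMI as an age-standardised score where a reference exists for the participant's age, and say how it is reported where none exists.

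**Cost.** The index and the contrast are derived from data already scheduled. The index is only as good as the height measure, which is difficult with contractures or scoliosis. It reduces growth effects without fully removing them, because lean mass per height squared need not be constant as a child grows. The contrast of changes loses precision relative to a simple pre-post comparison (Step 4), so the sponsor should check what difference 44 participants can detect with it.
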